# 1 INTRODUCTION

MCC18914 is a nonrandomized, phase II, single arm, multicenter trial evaluating safety and efficacy of thoracic radiation therapy followed by nivolumab and ipilimumab in participants with Extensive-Stage Disease Small Cell Lung Cancer (ED-SCLC) who have completed a first-line platinum-based chemotherapy regimen and achieved ongoing complete response (CR), partial response (PR), or stable disease (SD). This study will determine whether nivolumab and ipilimumab delivered 2 weeks following consolidative thoracic radiation therapy demonstrates acceptable toxicity and whether the treatment regimen will improve 6-month progression-free survival (PFS) compared with a similar historical control cohort in this participant population. Additional objectives include further characterization of overall survival, adverse event profile, patterns of failure analysis, and potential predictive biomarkers of response to nivolumab in combination with ipilimumab and thoracic radiation therapy in patients with ED-SCLC.

## 1.1 Study Rationale

### 1.1.1 Rationale for Investigating First-Line Maintenance Therapy in SCLC

SCLC accounts for 15 to 20% of new cases of lung cancer and is associated with poor outcomes. SCLC is traditionally classified as Limited Stage Disease (LD-SCLC: TNM stages I to IIIB) and Extensive Stage Disease (ED-SCLC: TNM stage IV with distant metastases (M1) including malignant pleural effusions). For LD-SCLC, a combined therapeutic approach of radiotherapy, chemotherapy and (rarely) surgery is used with curative intent[1]. Most patients at diagnosis have ED-SCLC and are treated with four to six cycles of etoposide plus platinum-based therapy (EP), which remains the standard chemotherapy regimen for LD- and ED-SCLC[2]. Overall survival (OS) remains poor with median survival for LD-SCLC at 18 to 30 months[3] and for ED-SCLC in the range of 9 to 12 months[4-7]. Despite high initial response rates, in particular in patients with ED-SCLC, the disease does recur or progress rapidly after completion of chemotherapy, with median PFS of only 2-3 months[7, 8]. A Dutch randomized phase III of patients with ED-SCLC treated with thoracic radiation therapy following EP reported a significant improvement in PFS at 6 months (24% vs 7%, HR 0.73) and a significant improvement in 2 year OS (13% vs 3%, p=0.004) with the addition of thoracic radiation therapy[5]. There are no other established standard of care treatments for subjects with ED-SCLC who complete first line therapy with EP and have achieved stable disease or response. In a phase 3 trial of topotecan versus observation, topotecan did not show an OS prolongation for SCLC patients after completion of EP[8]. Recently, sunitinib showed an improved PFS in a Phase 2 trial of sunitinib vs placebo in SCLC patients after completion of EP[7]. Despite the extensive chemotherapy regimens administered to ED-SCLC patients, approximately 75-90% of patients have persistent intrathoracic disease and though consolidative RT alone to the residual thoracic disease can improve time to progression in the thorax, 2 year OS is still only 13% among patients treated with TRT [5]. This underscores the need for more effective treatment options in this devastating malignancy.

Considering the short median OS for patients who have completed first line platinum-based treatment, as well as the even shorter PFS experienced in this disease, new treatments complementary to SCLC standard first-line platinum-based treatment are required.

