### 2.2 Secondary Objectives

1. To estimate the median PFS among patients treated with ipilimumab and nivolumab with thoracic radiotherapy (30 Gy in 10 fractions) after standard treatment with 4-6 cycles of platinum-based chemotherapy.
2. To estimate 1-year OS rate among patients treated with ipilimumab and nivolumab with thoracic radiotherapy after standard treatment with 4-6 cycles of platinum-based chemotherapy.
3. To estimate median OS among patients treated with ipilimumab and nivolumab with thoracic radiotherapy after standard treatment with 4-6 cycles of platinum-based chemotherapy.

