Screening		Week 0	± 28 days
Baseline (RECIST 1.1)		Week 4 (prior to initiation of ipilimumab/nivolumab)	+/- 5 days
Between Week 10 and Week 35	Every 8-9 weeks after initiation of Nivolumab/Ipilimumab	10,19,27,35,	± 5 days
Beyond Week 35	Every 12 weeks	47,59,71+,	± 5 days

A-Acceptable Radiographic Tumor Assessments:

---CT/ Chest-With IV contrast preferred.

---CT/MRI Abdomen-With oral and IV contrast preferred.

---CT/MRI Pelvis-With oral and IV contrast preferred. Only required if patient has known pelvic visceral metastases or bony metastases in the pelvis.

**Table 7.4-2.** Schedule of MRI/CT Brain Surveillance Assessments A

Time On Study	Assessment Frequency	Assessment Week (Day 1 of Week Shown)	Assessment Window
Screening/Baseline		Week 0	Within 28 days
Week 10	Every 12-13	Weeks 10, 23, 35, 47,59+	±5 days

	weeks	
--	-------	--

A-MRI/CT Brain-with contrast if possible. MRI preferred.

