## 9.2 Phase I/II Sample Size Determination

We propose a single arm, non-randomized phase I/II study, with the goal to evaluate efficacy compared to historical controls. Slotman et al. [5] reported a 6-month progression-free survival (PFS) of 24% with platinum-based chemotherapy and thoracic radiation therapy. We would propose to pursue a phase III randomized controlled study if there is a 20% improvement in 6-month PFS with the addition of combined immune checkpoint blockade as part of the proposed clinical study. Therefore, this regimen would be considered not worthwhile to pursue if the true 6-month PFS is 24% or less and worth pursuing if the true 6-month PFS is 44% or greater. The trial will use a Simon's 2-stage design[49] with 1-sided 0.05 level type I error and 90% power. The total target sample size is 52 patients. During the 1st stage, 18 patients will be accrued. If 4 or fewer patients have not progressed at 6 months, the study will be closed for futility. However, if at least 5 patients have not progressed at 6 months, then the study will continue to accrue an additional 34 patients. Once the total number of patients has accrued (n=52), then the null hypothesis will be rejected if at least 18 patients have not progressed at 6 months. In order to accommodate censoring, we may increase the total sample size by up to 10% (n=57).

- The final PFS analysis is targeted to occur 6 months after the last participant is enrolled
- The final OS analysis is targeted to occur 1 year after the last participant is enrolled.

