## 9.4 Endpoints

### 9.4.1 Primary Endpoints

**Part I: Safety Run In Phase I:** Unacceptable toxicity status at the end of 13-week safety observation period with unacceptable toxicity defined as:

- Any grade 4 immune related adverse event (irAE),
- Any  $\geq$  grade 3 noninfectious pneumonitis,
- 
- Any grade 3 irAE, excluding pneumonitis, that does not downgrade to grade 2 within 7 days after onset of the event despite optimal medical management including systemic corticosteroids or does not downgrade to  $\leq$  grade 1 or baseline within 14 days,
- Liver transaminase elevation  $> 8 \times$  ULN or total bilirubin  $> 5 \times$  ULN,
- Any  $\geq$  grade 3 non-irAE, except for the following exclusions:
  - grade 3 fatigue lasting  $\leq$  7 days
  - grade 3 endocrine disorder (thyroid, pituitary, and/or adrenal insufficiency) that is managed with or without systemic corticosteroid therapy and/or hormone replacement therapy and the participant is asymptomatic
  - grade 3 infusion-related reaction (first occurrence and in the absence of steroid prophylaxis) that resolves within 6 hours with appropriate clinical management
  - grade 3 or 4 neutropenia that is not associated with fever or systemic infection that improves by at least 1 grade within 3 days.

**Part II: Phase II:** The primary endpoint is 6-month PFS status. PFS is defined as the duration from date of registration to date of first documentation of progression assessed by local investigator or symptomatic deterioration (as defined above) or death due to any cause. Patients last known to be alive without report of progression are censored at date of last disease assessment. For patients with a missing scan (or consecutive missing scans) whose subsequent scan determines progression, the expected date of the first missing scan (as defined by the disease assessment schedule) will be used as the date of progression.

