### **9.5.2 Efficacy Analyses**

At the PFS analysis time point, primary PFS analyses will be conducted. The PFS curve, PFS median with 95% CIs, and PFS rates at 6 and 12 months with 95% CIs will be estimated using Kaplan-Meier methodology.

At the OS analysis time point, the OS analyses will be conducted. OS curves, OS medians with 95% CIs, and OS rates at 12 and 24 months with 95% CIs will be estimated using Kaplan-Meier methodology.

Additionally, at the same time point as the primary OS analysis, PFS curves, PFS medians with 95% CIs, and PFS rates at 6 and 12 months with 95% CIs will be estimated using Kaplan-Meier methodology.

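### At the trial's own null, the Kaplan-Meier median PFS tends to land on the Week 10 or Week 19 scan and overstates time to progression by about 0.5 to 1.2 months on average; an interval-censored estimate should sit beside it

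*Combined protocol and SAP*

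**What the plan says.** - **Role of the median.** The first objective in Section 2.2 is "To estimate the median PFS among patients treated with ipilimumab and nivolumab with thoracic radiotherapy". The primary endpoint is 6-month PFS status (Section 9.4.1).
- **Background figure.** Section 1.1.1 says that patients with this disease "progress rapidly after completion of chemotherapy, with median PFS of only 2-3 months". This comes before the text turns to thoracic radiotherapy.
- **Null and target.** In Section 9.2 the cited phase III trial "reported a 6-month progression-free survival (PFS) of 24% with platinum-based chemotherapy and thoracic radiation therapy", and the regimen is "worth pursuing if the true 6-month PFS is 44% or greater". No expected median is stated for this trial.
- **Scans.** Table 7.4-1 puts body scans at Weeks 4, 10, 19, 27 and 35, the later ones described as "Every 8-9 weeks after initiation of Nivolumab/Ipilimumab". Table 7.4-2 puts brain scans at Weeks 10, 23 and 35. No tumor scan is therefore scheduled between Weeks 10 and 19. Section 7.4 allows extra scans when clinically indicated and does not say how often to expect them.
- **Event date.** Section 9.4.1 runs PFS from registration to the "date of first documentation of progression assessed by local investigator", symptomatic deterioration or death. A back-dating rule applies only when a scheduled scan was missed.
- **Estimator.** Section 9.5.2: "PFS median with 95% CIs, and PFS rates at 6 and 12 months with 95% CIs will be estimated using Kaplan-Meier methodology". No interval-censored or sensitivity analysis is planned.

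**The concern.** A progression that happens between two scans is recorded at the later one. When the gap is long relative to the median, the Kaplan-Meier curve drops mainly at scan dates, and its median and confidence limits tend to sit on those dates. The missing-scan rule does not help, because the 9-week gap is planned and no scan is missed.

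In a randomized trial with a common schedule, both arms would share this shift. Here there is one arm and no concurrent control to absorb it. What is at stake is the meaning of the first secondary result: the reported median may describe when scans took place more than when disease progressed.

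**Working it through.** **1. The plan's own figure.** Section 9.2 states: "The trial will use a Simon's 2-stage design[49] with 1-sided 0.05 level type I error and 90% power". It continues past stage 1 with at least 5 of 18 progression-free and rejects with at least 18 of 52. The exact rejection probability is P(reject | p) = Σ(x = 5 to 18) Bin(x; 18, p) × P(Y ≥ 18 − x), with Y ~ Bin(34, p).
- p = 0.24: 0.0494.
- p = 0.44: 0.9035.

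The design reproduces. The rule counts 6-month status and does not use the median.

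**2. Median implied by the null (constant hazard assumed).**
- Hazard = −ln(0.24)/6 = 0.238 per month.
- Median = 6 × ln 2 / −ln(0.24) = 2.91 months, or 12.7 weeks.
- For 44%: 6 × ln 2 / −ln(0.44) = 5.07 months.

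**3. Where the scans fall.** Scans are timed from radiotherapy start, PFS from registration. Day 1 of Week 10 can mean 9 or 10 elapsed weeks, and Day 1 of Week 19 can mean 18 or 19. The lag from registration to radiotherapy is not given, so it is varied. Times are months from registration.

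| Assumed lag | Week 10 scan | Week 19 scan | Position of 2.91 |
|---|---|---|---|
| 0 days | 2.07-2.30 | 4.14-4.37 | inside the gap |
| 14 days (+0.46) | 2.53-2.76 | 4.60-4.83 | inside the gap, near Week 10 |
| 28 days (+0.92) | 2.99-3.22 | 5.06-5.29 | just before Week 10 |

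True PFS at the Week 10 scan is exp(−0.238 × t). This is 58-61% with no lag, so the curve usually crosses 50% at Week 19. With a 14-day lag it is 52-55%, so the crossing is close to a coin toss between the two scans. With a 28-day lag it is 47-49%, so the crossing is usually at Week 10.

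**4. Simulation at the 24% null.** Trials of 52 patients were simulated with exponential PFS, scans at Table 7.4-1 times ±5 days, no censoring and both week readings (3,000 to 20,000 trials per setting). The share of events dated when they occur (death, symptomatic deterioration) is not in the documents; it was varied from 0 to 30%.

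| Setting | Typical (median) reported Kaplan-Meier median, months |
|---|---|
| No lag, 0-30% exact | 4.0-4.3 |
| Fixed 14-day lag, 0% exact, Week 10 = 10 elapsed weeks | 4.7 |
| Fixed 14-day lag, 30% exact | 3.0-3.7 |
| Uniform 0-28-day lag, 15% exact | 3.35 or 4.17, by week reading |
| Fixed 28-day lag | 3.1-3.3 |

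The mean over trials was about 3.45 to 4.1 months against a true 2.91, above the truth in every setting. The bias is 3.45 − 2.91 = 0.54 to 4.1 − 2.91 = 1.19 months. Mean and typical values differ because the reported median clusters at two scan dates.

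**5. Sensitivity.**
- True 44% (median 5.07): mean reported median 5.6-6.0 months, also upward in every setting.
- No lag, true median 2.0 months (8.7 weeks, before the Week 10 scan): typically reported at 2.2-2.4.
- No lag, true median 2.5 months: 4.05-4.2 if all events are scan-dated, 2.8-3.45 if 30% are exact.
- Non-constant hazard with 24% at 6 months (no lag, 10 elapsed weeks, all scan-dated): Weibull shape 0.8 has a true median of 2.43 and a 54% chance of a reported median above 3.5 months; shape 1.2 has 3.29 and 97%.
- Unscheduled scans finding an assumed 30-50% of progressions, with 0-14-day lag and 15-30% exact events: 3.4-3.8 months.
- An interval-censored Weibull fit (0-14-day lag, 15% exact) gave 2.90 and 5.16 for true 2.91 and 5.07. The data were exponential, a special case of the Weibull, so this does not test misspecification.

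**The case against.** The strongest case for leaving the plan alone has four parts.

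- **Kaplan-Meier estimates what the plan defines.** Section 9.4.1 makes the event date the first documentation, and Kaplan-Meier is the conventional estimator for it. This stands. It argues for keeping the Kaplan-Meier median, not against a supportive estimate of the underlying time.
- **The 2.9-month value depends on constant hazard.** Sections 1.1.1 and 1.1.4 give 24% against 7% with a hazard ratio of 0.73, yet proportional hazards would give 0.07^0.73 = 14%. Starting from 7% and 0.73 under constant hazard, the median is 1.56/0.73 = 2.14 months (9.3 weeks). That is close to the Week 10 scan with no lag, and nearly all settings examined there reported 2.2-3.1 months. This stands as a limit on the size of the effect.
- **Nothing planned uses the comparison.** Section 2.2 only estimates the median, and no passage tests it against 2-3 months. This also stands.
- **Lag, exactly dated events and unscheduled scans soften the effect.** They do. In the settings that varied lag and exact dating at the 24% null, the mean bias stayed upward.

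A reader might infer that the whole 2-3 month range lies in the gap, that about 4 months is the usual report, and that an inactive regimen would therefore appear to lengthen the median. The documents do not support this. Two months falls before Week 10 when counted from radiotherapy start. The typical reported median at the null runs from about 3.0 to 4.7 months. The documents also do not say how the 2-3 months or the 24% were dated; if those figures are scan-dated too, they may carry a similar shift.

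**Conclusion.** The point holds in a limited form. If true 6-month PFS is 24% and the hazard is roughly constant, the planned median is biased upward as a measure of time to progression by about 0.5-1.2 months on average, or 0.54/2.91 = 19% to 1.19/2.91 = 41%. Where it lands depends mainly on the unstated lag and on the share of events dated exactly. The figures assume 52 patients, no censoring and no unscheduled scans unless stated. For a true median near 2 months with no lag the typical shift is small.

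The go/no-go rule is untouched. Whether the background figure has the same bias cannot be settled from the documents, so no claim of false benefit follows. This is worth correcting in the analysis plan and is no reason to question the design.

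**What to change.** In Section 9.5.2:

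- Keep the Kaplan-Meier curve and median as planned.
- Add, as a prespecified supportive analysis, an interval-censored estimate of median PFS with a 95% CI: the Turnbull estimate plus a Weibull or piecewise-exponential fit. Place each radiographic progression between the last scan without progression and the first scan with it. Treat deaths and symptomatic deterioration as exact.
- Report the scan interval that contains the Kaplan-Meier median, so that readers can see how coarsely it is located.

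The cost is SAP wording and one extra analysis on scan dates already collected, with no change to visits or treatment. The parametric fit adds a mild assumption, which is why the Turnbull estimate should accompany it. The supportive median will usually be shorter than the Kaplan-Meier one, so its role should be fixed before the data are seen.

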## 1.1.2 Rationale for Immuno-Oncology Therapeutic Approaches in SCLC

SCLC has classically been associated with immune-mediated paraneoplastic processes, such as cerebellar degeneration, limbic encephalitis and Lambert-Eaton myasthenic syndrome [9]. For example, antibodies generated against human neuronal RNA-binding proteins (e.g. Hu), which are expressed on neurons and SCLC tumors, leads to an encephalomyelitis [10]. Interestingly, SCLC patients that present with these ‘early’ paraneoplastic syndromes have a more favorable prognosis [11, 12], suggesting that an underlying immune response is being generated against these onconeural antigens.

Proof of an active immune environment in SCLC has been described in a few analyses of patient samples. First, analysis of sixty-four SCLC tumors demonstrated that a wide range of CD45+ cells infiltrated the tumor, an average of 40 immune cells/field, and that high CD45+ counts were associated with a better prognosis [13]. Secondly, a separate study found that various tumor-infiltrating lymphocyte (TIL) subsets were present in SCLC brain metastases and that programmed death ligand 1 (PD-L1) was heterogeneously expressed [14]. Finally, evaluation of peripheral blood cells in 35 SCLC patients demonstrated a high CD4+ effector T cell to T regulatory (Treg) cell ratio in patients with LD-SCLC vs. ED-SCLC [15]. This implies that in some respect, SCLC pathology integrates with the immune response.

Furthermore, SCLC is known to have one of the highest mutational loads [16], which is thought to be a reflection of myriad insults inflicted by carcinogens from smoking. Additionally, comprehensive genomic profiling of SCLC tumors has identified that the vast majority lack functional p53 (90%) and Rb1 (65%) [17]. This universal genetic aberration facilitates poor genomic stability [18], thus perpetuating the generation of tumor-associated antigens (TAAs). Interestingly, recent studies have highlighted that the clinical efficacy of cytotoxic T-lymphocyte-associated antigen 4 (CTLA-4) and programmed death 1 (PD-1) blockade in melanoma and non-small cell lung cancer (NSCLC), respectively, are partially driven by the mutational burden of the tumor and the presence of neoantigens [19, 20]. Thus, the high mutational burden in SCLC may facilitate enhanced immune recognition. Though SCLC pathology appears to be intertwined with the immune response and is predisposed by a substantial mutational load, prior evidence indicates that major histocompatibility complex (MHC) surface expression is reduced in SCLC [21, 22], which may preclude robust immune recognition.

These data support the notion that there is an active immune microenvironment within primary and metastatic SCLC lesions. Finally, a phase I/II non-randomized trial (CheckMate 032) evaluated nivolumab with or without ipilimumab in LD-SCLC/ED-SCLC patients that failed platinum-based therapy. This study reported a response rate of 23% at the most efficacious dose level of ipilimumab 3mg/kg and nivolumab 1mg/kg. This study also reported a tolerable safety profile for patients treated at the aforementioned dose level. Considering the immune response seen in SCLC patients, and the results of early phase studies utilizing checkpoint inhibitors nivolumab and ipilimumab in SCLC patients in later treatment lines, it is reasonable to expect that nivolumab and ipilimumab combination therapy are likely to also provide benefit as first line maintenance therapy in SCLC.

## 1.1.3 Rationale for Nivolumab (1 mg/kg)/Ipilimumab (3 mg/kg) Combination in SCLC

In a phase I/II study of nivolumab and nivolumab/ipilimumab for treatment of recurrent SCLC (CA209032), participants who were platinum sensitive or refractory and had progressive disease were enrolled regardless of

tumor PD-L1 status or number of prior chemotherapy regimens [23]. This open-label study randomized participants to nivolumab 3 mg/kg IV every 2 weeks or nivolumab + ipilimumab (1 + 1 mg/kg, 1 + 3 mg/kg or 3 + 1 mg/kg) IV every 3 weeks for 4 cycles followed by nivolumab 3 mg/kg every 2 weeks. The primary objective was objective response rate. Other objectives were safety, PFS, OS and biomarker analysis.

All participants had prior platinum-based first-line treatment and progression after the most recent treatment regimen. Baseline characteristics were typical for a SCLC population with respect to age, smoking history, and gender.

**Safety.** While the incidence of drug-related adverse events (AEs) in the nivolumab 1 mg/kg/ipilimumab 3 mg/kg cohort (79% any grade, 30% grade 3-4) was higher than in the nivolumab monotherapy group (53% any grade, 13% grade 3-4), the treatment discontinuation rate for treatment-related AEs was only 11% (nivolumab 1 mg/kg / ipilimumab 3 mg/kg): 5 patients with diarrhea, myasthenia gravis [subsequently developing complications with fatal outcome], pneumonitis, cardiomyopathy, and 1 patient with hypothyroidism, hyperglycemia, and increased ALT levels).

The most frequent ( $\geq 10\%$ , any grade) drug-related AEs were diarrhea, fatigue, rash, pruritus, hypothyroidism, rash maculo-papular, nausea, hyperthyroidism, and increased lipase levels. One treatment-related death in the nivolumab 1 mg/kg / ipilimumab 3 mg/kg cohort occurred. This participant developed myasthenia gravis (reported as grade 4) after treatment start and suffered from complications resulting in death. Limbic encephalitis was reported in 3 participants, which resolved with immunosuppressive treatment in 2 cases. Another participant had a minor response to immunosuppressive treatment and eventually died due to the underlying tumor disease.

**Efficacy.** Patients treated at the recommended phase III dose of ipilimumab 3mg/kg and nivolumab 1mg/kg (n=61) were noted to have an overall response rate (ORR) of 23%, and the disease control rate (CR + PR + SD) was 44%. Objective responses were long lasting, with a median duration of response of 7.7 months in the nivolumab 1mg/ipilimumab 3 mg combination group. The median PFS was 2.6 months (95% CI: 1.4, 4.1) The median OS was 7.7 months (95% CI: 3.6, 18) in the nivolumab 1 mg /ipilimumab 3 mg combination group, which compares favorably with historical controls [8]. There is an ongoing phase III randomized, placebo-controlled study (CA209-451) evaluating PFS and OS among patients with ED-SCLC with at least stable disease after 4 cycles of EP chemotherapy. More than 800 patients are to be randomized to placebo, nivolumab 240 mg delivered every 2 weeks, or ipilimumab 3 mg + nivolumab 1 mg combination therapy for 4 cycles followed by nivolumab 240 mg every 2 weeks until progression. Patients will be carefully monitored on this protocol, and we expect results from our study with comparable inclusion criteria to be available in the coming years.

